4.3 Accountability Records for Investigational Product

68Ga-PSMA-11 will be provided by the Department of Radiology and Biomedical Imaging Radiopharmaceutical Facility. Upon receiving the investigational product, a certified Nuclear Medicine technologist will perform dose calibration and complete the radio pharmacy log. Any unused investigational products will be disposed of according to local radiation safety guidelines.

4.4 Ordering Investigational Product

68Ga-PSMA-11 will be obtained directly from the UCSF Department of Radiology and Biomedical Imaging Radiopharmaceutical Facility.

5 Study Procedures and Schedule of Events

The study-specific procedures and assessments are detailed in this section and outlined in the Study Calendar – Section 5.1.

On-study procedure or visit delays for public holidays, public emergencies, or weather conditions do not constitute a protocol violation.

5.1 Study Calendar

5.1.1 Study Calendar for Sub-Cohort A1

Period / Procedure	Screening (Within 12 weeks prior to C1D1)	Cycle 1 Day 1 (Start of systemic therapy) ¹⁰	Follow up Response Monitoring 8 weeks (+/- 4 weeks)	Follow up PET 16 weeks (+/- 8 weeks) Following Treatment Initiation ⁹	Disease Progression by PCWG3
Informed consent	X				
Baseline conditions	X				
Concomitant medications	X				
Demographics	X				
Serum PSA ¹	X		X	X	X
Performance status	X				
LDH, CBC + diff, Liver function tests	X				
Disease assessment by cross sectional imaging	X ²		X ³	X ⁴	X ⁴
⁶⁸ Ga-PSMA-11 PET/CT or PET/MRI	X ⁸			X	X (Optional)
Tumor biopsy ⁵ (optional)	X				
Circulating tumor nucleic acid collection ⁶ (optional)	X			X	X
FDG PET/CT ⁷ (optional)	X				

¹ Response monitoring with respect to serum PSA will occur per standard of care and provider discretion. A minimum of three serum PSA values are required including: at baseline prior to initiation of systemic treatment (+/- 12 weeks), at 8 weeks (+/- 4 weeks), and at 16 weeks (+/- 8 weeks).

² Cross-sectional imaging of the chest/abdomen/pelvis (CT or MRI; with IV contrast if medically permissible), including paired CT or MRI obtained with baseline PET scan.

³ Response monitoring with respect to conventional imaging will occur per standard of care and provider discretion.

⁴ Cross-sectional imaging of the chest/abdomen/pelvis (CT or MRI; with IV contrast if medically permissible), including paired CT or MRI obtained with PET scan. Patients who underwent PET/CT at baseline should have same imaging modality performed during follow-up, and likewise patients who underwent PET/MR at baseline should have same imaging modality performed for follow up PSMA PET imaging.

⁵ Metastatic tumor biopsy is optional for [eligible](#) participants. Tumor biopsy should be performed within 12 weeks following baseline PET. Soft tissue, PET-avid lesions should be prioritized for biopsy whenever feasible. Biopsy will be performed under companion protocol CC# 155518.

⁶ Circulating tumor nucleic acid collection via peripheral blood collection is optional. Collection will be performed under companion protocol CC # 155518.

⁷ FDG PET/CT is optional. FDG PET will be performed at baseline (+/ 12 weeks from date of baseline Ga-PSMA PET).

⁸ At least one metastatic lesion with PSMA uptake at or above that of the blood pool will be required for study entry. A ⁶⁸Ga-PSMA-11 PET/CT or PET/MRI obtained prior to study entry may serve as the patient's baseline PSMA PET scan if within 12 weeks of C1D1 (start of systemic therapy).

⁹ Specific timing of follow up PET to be determined based on modality of therapy (see Section 5.3.6).

¹⁰ Patients started on systemic therapy during the screening period/prior to study enrollment will be transitioned to sub-cohort A2.

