1.4 Rationale for Inclusion of Optional Paired Tumor Biopsy and FDG-PET

Whereas PSMA is uniformly expressed in the early prostate cancer, variable levels of PSMA expression have been reported in patients with castration-resistant disease.²¹ PSMA expression is inversely related to neuroendocrine biomarker genes,²¹ and treatment-emergent small-cell neuroendocrine prostate cancer (SCNC) may present as a low-uptake lesion on PSMA-based imaging.²² Additionally, up to 25% of patients screened for enrollment in PSMA-targeted radioligand therapy fail to meet inclusion criteria due to low- or heterogeneous-PSMA expression.^{11,12,23} “Discordant” metastases on serial Ga-PSMA- and FDG-PET imaging, with low PSMA and high Fluorodeoxyglucose (FDG) uptake, have also been described. Limited existing data on this subset of patients suggests a particularly aggressive cancer phenotype,²³ however the histologic and genomic features of this disease entity have yet to be defined. Furthermore, heterogeneous treatment effect and/or prior localized therapy may also contribute to intra-patient variations in PSMA expression. To address this and to better differentiate treatment-related PSMA suppression from discordant disease, we will offer an optional FDG-PET scan to patients with low- or heterogeneous PSMA uptake.²⁴ Additionally, we will offer optional paired tumor biopsies in selected patients with low PSMA expression, or heterogeneous PSMA uptake on Ga-PSMA PET imaging. As the use of Ga-PSMA PET imaging in mCRPC increases, there is an urgent need to better characterize these different patterns of PSMA expression. By quantifying variations in PSMA expression levels in patients with mCRPC, Ga-PSMA PET may offer non-invasive molecular insight into the underlying biology of advanced prostate cancer.

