2.4 Exploratory (Correlative) Objectives

Exploratory Objective
1. To descriptively characterize the histologic, transcriptional, and genomic features of PSMA low/negative lesions among patients who undergo paired optional metastatic tumor biopsy.
2. To descriptively characterize the relationship between $SUV_{max-ave}$ on baseline Ga-PSMA PET with optional baseline FDG-PET.
3. To determine whether heterogeneity of PSMA expression on baseline Ga-PSMA PET is associated with overall survival.
4. To descriptively characterize the patterns of PSMA expression at the time of disease progression among patients who undergo optional PSMA PET.
5. To determine whether the percent change from baseline in PSMA PET is associated with PSA50 response among subgroups of patients defined by treatment modality received, including AR targeting treatment, PSMA-targeting radioligand therapy, cytotoxic chemotherapy, and immunotherapy.

3 Study Design

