3.3.1 Inclusion Criteria

1. Sub-cohort A1: Patients must have baseline evaluations performed within 12 weeks prior to the start of systemic therapy. (*Note: Patients in sub-cohort A1 who initiate systemic therapy during the screening period/prior to study enrollment may be re-consented to transition to sub-cohort A2.*)
2. Sub-cohort A2: Patients must meet **all** the following requirements:

- Have had a baseline pre-treatment 68Ga-PSMA-11 PET scan and PSA measurement performed within 12 weeks prior to the start of current systemic therapy.
- Able to have an on-treatment 68Ga-PSMA-11 PET and a PSA measurement within 16 weeks (+/- 8 weeks) after the start of current systemic therapy.

Note: The screening period for sub-cohort A2 is within 24 weeks after the patient started their current systemic therapy.

3. Patients must have progressive castration resistant prostate cancer, according to PCWG3 criteria.
4. Patients must have planned initiation of systemic treatment (sub-cohort A1), or ongoing systemic treatment (sub-cohort A2) for castration resistant prostate cancer within 12 weeks of baseline Ga-PSMA PET.
5. Patients must have at least one metastatic lesion with PSMA uptake at or above the blood pool on their baseline PSMA PET scan.
6. The patient must be able and willing to comply with study procedures and provide signed and dated informed consent.
7. Patient must have an Eastern Cooperative Oncology Group (ECOG) Performance Status of 0 or 1.
8. Patient must be Aged 18 years or older at the time of study entry
9. Patients who undergo optional metastatic tumor biopsy following completion of baseline Ga-PSMA PET (sub-cohort A1) must additionally meet all of the following criteria:
 - Presence of one or more metastases by standard radiographic scans that is safely accessible to tumor biopsy in the judgment of treating clinician and/or Interventional Radiology.
 - No history of radiation therapy to the target metastatic lesion selected for tumor biopsy
 - No contra-indication to biopsy including uncontrolled bleeding diathesis.
 - Platelets >75,000/ μ L and PT or INR and a PTT < 1.5 times the institutional ULN within 14 days prior to biopsy

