5.3.2 Baseline ^{68}Ga -PSMA-11 PET/MRI or PET/CT

- ^{68}Ga -PSMA-11 PET/CT or PET/MRI
 - Participants will begin PET imaging between 55 and 70 minutes after the injection of Ga-PSMA-11 at a dose of 3-7 mCi.
 - A dose of 20 mg of furosemide (Lasix) is recommended to be injected intravenously together with, shortly before, or after, administration of the radiotracer in order to minimize PET scatter artifacts from excreted radiotracer accumulation in the kidney and urinary bladder that can occur with the gallium-68 radionuclide. Furosemide should not be administered in patients with medical contraindications to Furosemide.
 - Contrast agent for MRI or CT will be administered as clinically indicated.
 - Participants will be monitored for adverse events for two hours after Ga-PSMA-11 administration.
 - A formal radiology report from the imaging scan will be generated by the Nuclear Medicine department. If any unexpected findings are visualized, these will be reported to the treating health care provider, who will then contact the patient if additional work-up needs to be performed.
 - If the patient has received a ^{68}Ga -PSMA-11 PET scan prior to study enrollment and within 12 weeks prior to the start of current systemic therapy (sub-cohort A2), the PET scan may serve as the baseline PET scan and does not need to be repeated at screening.

5.3.3 Baseline Tumor Biopsy and Circulating Tumor Nucleic Acid Collection (Optional – Within 12 weeks of Baseline PSMA PET)

Patients in sub-cohort A1 will undergo optional metastatic tumor biopsy and circulating tumor nucleic acid collection within 12 weeks of baseline PSMA PET scan. Biopsy and/or circulating nucleic acid collection will be performed under protocol CC # 155518. Soft tissue lesions with low/negative PSMA uptake will be prioritized for tissue acquisition. However, either bone or soft tissue lesions that are deemed safely accessible per Interventional Radiology assessment will be potentially considered for imaging.

Optional circulating tumor nucleic acid collection under companion protocol CC# 155518 will also be performed at the following times:

- Initiation of systemic treatment
- Disease progression

5.3.4 Baseline FDG PET (Optional for sub-cohort A1 only – within 12 weeks of Baseline PSMA PET)

Patients in sub-cohort A1 may undergo optional FDG PET/CT scan (within 12 weeks after date of baseline Ga-PSMA PET) per standard imaging procedures.

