7.1 Imaging Analysis

A trained nuclear medicine physician will evaluate the reconstructed PET, CT or MRI, and fused PET/CT or PET/MR images using a PET volume computer-assisted reading software package. A positive lesion on PET will be defined as a focus of activity with higher SUV compared with mediastinal blood pool that is not attributable to other etiologies of tracer distribution (e.g. inflammation, excretion). A volume of interest (VOI) will be semi-automatically placed around each lesion, and the calculated maximum standard uptake value (SUV_{max}) will be recorded for each lesion, including lesions that are detected on standard scans but are not positive on PET. Adjusted SUV_{max} data will then be averaged the primary tumor and 5 largest lesions in each of three metastatic site (nodal, visceral, and osseous) within a given patient, up to a maximum of 16 lesions per patient ($SUV_{max-avg}$). Irradiated lesions will be excluded from this analysis.

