7.4.3 Secondary Analysis (or Analysis of Secondary Endpoints)

The study cohort will be dichotomized by the median with respect to percent change from baseline in $SUV_{max,ave}$ on PSMA PET. The time-to-event variables including PSA progression-free defined by PCWG3, and overall survival will be compared between dichotomized subgroups using the log-rank test. Kaplan-Meier product limit method will be used to estimate median survival in each subgroup.

Amongst the subset of measurable soft tissue lesions by RECIST 1.1 criteria, on a per-lesion basis, the mean percent change from baseline in SUV_{max} on PSMA PET will be compared between responding lesions by RECIST 1.1 criteria vs. those without response, using Mann-Whitney test.

PSMA negative lesions will be defined as those with SUV values below the mediastinal blood pool. Low positive lesions will be defined as those with SUV_{max} values above the blood pool, but below background liver uptake. Intermediate positive lesions are those defined by SUV_{max} values above background liver, but below parotid gland uptake. High positive lesions are those with SUV_{max} values above that of parotid gland. The histologic, genomic and transcriptional features of each subgroup of PSMA lesion category that has matching tumor tissue will be descriptively reported with particular emphasis on the low and negative PSMA lesions that have paired tumor tissue available.

The median and range for inter-tumoral SUV_{max} across metastatic lesions within individual patients will be descriptively reported, to assess for heterogeneity of PSMA uptake. The cohort will be dichotomized above and below median range of SUV_{max} values to define low and high heterogeneity subgroups. Overall survival from date of onset of mCRPC will be compared between high vs. low heterogeneity subgroups.

Analysis of the correlation between SUV_{max} PSMA and FDG PET will be performed on a per-lesion basis amongst the subset of patients who have paired evaluable imaging using Pearson r correlation coefficient.

Patterns of PSMA expression at the time of progression by PCWG3 criteria will be descriptively characterized.

Comparison of mean percent change from baseline in $SUV_{max,ave}$ in PSA50 responders vs. non-responders will be performed in pre-specified subgroups based on modality of systemic

treatment, including AR targeted therapy, PSMA-directed radioligand therapy, cytotoxic chemotherapy, and immunotherapy.

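### The A1 calendar and Section 5.3.3 give opposite biopsy priorities for PSMA-negative lesions, which exploratory objective 1 needs

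*Combined protocol and SAP*

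**What the plan says.** Two places in the protocol tell staff which lesion to favour for the optional metastatic biopsy in sub-cohort A1.

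- Section 5.1.1, footnote 5: "Soft tissue, PET-avid lesions should be prioritized for biopsy whenever feasible".
- Section 5.3.3: "Soft tissue lesions with low/negative PSMA uptake will be prioritized for tissue acquisition". It adds that other bone or soft tissue lesions may be considered if Interventional Radiology finds them safely accessible.

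Both describe a biopsy within 12 weeks of the baseline PET, done under companion protocol CC# 155518.

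The purpose of the tissue is set out elsewhere. Section 1.4 says "we will offer optional paired tumor biopsies in selected patients with low PSMA expression, or heterogeneous PSMA uptake on Ga-PSMA PET imaging". Exploratory objective 1 in Section 2.4 is "To descriptively characterize the histologic, transcriptional, and genomic features of PSMA low/negative lesions among patients who undergo paired optional metastatic tumor biopsy". Section 7.4.3 plans a description of every PSMA category that has matching tissue, with the emphasis on the low and negative ones.

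On how the calendar relates to the text, the opening of Section 5 says only: "The study-specific procedures and assessments are detailed in this section and outlined in the Study Calendar".

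**The concern.** The two instructions rank lesions by different criteria, and for at least one type of lesion the criteria point in opposite directions. The biopsy exists largely to learn about lesions with little or no PSMA uptake. A team working from the calendar footnote would favour avid lesions, and a team working from Section 5.3.3 would favour those with low or absent uptake.

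Two things are at stake. First, wherever footnote 5 is followed and a patient has accessible soft tissue lesions of both kinds, the biopsy is steered away from negative lesions, and low-positive lesions get no preference over more avid ones. That reduces the tissue available for exploratory objective 1. Second, if different staff follow different sentences, the number of samples in each PSMA category depends partly on which page was read, and a reader of the results could not tell how the tissue was selected.

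**Working it through.** No arithmetic from the plan applies, and there is no stated figure to reproduce. The check sets the two rules against the protocol's own lesion definitions.

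**Step 1: the definitions.** Section 7.1: "A positive lesion on PET will be defined as a focus of activity with higher SUV compared with mediastinal blood pool". Section 7.4.3: "PSMA negative lesions will be defined as those with SUV values below the mediastinal blood pool". Section 7.4.3 then defines low (above blood pool, below liver), intermediate (above liver, below parotid) and high (above parotid). That makes four categories.

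**Step 2: what Section 5.3.3 favours.** Negative and low, which is two of the four. These are the same two categories that exploratory objective 1 names.

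**Step 3: what footnote 5 favours.** This depends on 'PET-avid', for which no tracer or threshold is given.

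| Reading of 'PET-avid' | Categories favoured by footnote 5 | Shared with Section 5.3.3 | Objective 1 categories left out |
|---|---|---|---|
| A. Positive on PSMA PET (Section 7.1, above mediastinal blood pool) | low, intermediate, high | low (1 of 2) | negative (1 of 2) |
| B. Above liver on PSMA PET (assumed; stated nowhere) | intermediate, high | none (0 of 2) | negative and low (2 of 2) |
| C. FDG-avid | not defined on the PSMA scale | compatible | none by the wording (0 of 2) |

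**Step 4: which reading is natural.** The sentence in footnote 5 just before the priority rule times the biopsy from the baseline PET, and Section 5.3.3 times the same biopsy from the baseline PSMA PET. FDG PET is optional and has its own footnote (7). PSMA PET is therefore the natural reading, and reading A uses the nearest term the protocol defines. Under A the conflict is strict for negative lesions: a lesion cannot lie both above and below blood pool. Low-positive lesions satisfy both rules.

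**Step 5: whether the choice can arise.** Inclusion criterion 5 (Section 3.3.1) says "Patients must have at least one metastatic lesion with PSMA uptake at or above the blood pool on their baseline PSMA PET scan". So an enrolled patient with a PSMA-negative lesion also has at least one lesion at or above blood pool. Apart from a lesion exactly at blood pool, that second lesion is PET-positive under Section 7.1. If both are soft tissue and safely accessible, footnote 5 puts the negative lesion behind and Section 5.3.3 puts it ahead. The patients with heterogeneous uptake to whom Section 1.4 offers the biopsy are those in whom this can happen. The calendar schedules the biopsy only at screening, so this protocol plans no later biopsy that would make up for the choice.

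**Step 6: precedence.** The opening of Section 5 describes the calendar as an outline of procedures detailed in the text. It does not say which prevails when they differ.

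**The case against.** The strongest case on the other side is that this is a small wording matter.

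- **Both rules are preferences.** Neither sentence forbids biopsy of any lesion, and Section 5.3.3 keeps other accessible lesions open. This is true, but choosing between lesions is exactly what a priority rule does, and these two order negative lesions oppositely.
- **Several conditions must coincide.** The patient must be in A1, accept the biopsy, and have negative and avid lesions that are both soft tissue, accessible and, under criterion 9, not previously irradiated. This stands, and it limits how often the conflict matters.
- **The calendar is a summary.** Section 5.3.3 is the detailed text and agrees with Sections 1.4, 2.4 and 7.4.3, so a careful reader has grounds to follow it. That is reasonable, but it is an inference. Footnote 5 is itself a selection instruction, and nothing subordinates it.
- **FDG may have been meant.** Section 1.4 offers FDG PET to the same kind of patient, with low-PSMA, high-FDG disease in mind. This cannot be excluded, and on that reading the rules are compatible. The footnote would then need to name the tracer, so a correction is needed either way.
- **Tissue from avid lesions is still used.** Section 7.4.3 describes all categories that have tissue. That stands: no category's description becomes invalid, and the loss is in the number of low and negative samples.
- **The companion protocol may settle lesion choice.** It may, and it is not among the documents. It would not remove the contradiction from this one.

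**Conclusion.** The concern holds. On the natural reading of 'PET-avid' as positive on PSMA PET, the two current instructions for the same biopsy rank PSMA-negative lesions in opposite order, and nothing says which governs. Footnote 5 then leaves out one of the two categories that exploratory objective 1 names. The range over the possible readings is none (FDG) to both (above liver, an assumed threshold).

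These counts describe the wording, not the amount of tissue lost. The documents give neither a number of biopsies nor the share of patients with accessible soft tissue lesions of both kinds, so no patient count can be derived. The consequence is limited to one optional, A1-only, descriptive exploratory objective; the primary and secondary objectives and the power statement are unaffected. The conclusion assumes that the companion protocol does not already impose its own selection rule. It is worth correcting because the biopsy is invasive, is done for this objective, and the correction is easy.

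**What to change.** 1. Reconcile footnote 5 of Section 5.1.1 and Section 5.3.3 to a single target-lesion rule. The choice is for the investigators; it should be consistent with exploratory objective 1 and checked against companion protocol CC# 155518.
2. If 'PET-avid' is kept, define it by tracer and by threshold.
3. Link each biopsy explicitly to the SUVmax recorded for that lesion under Section 7.1 and to its Section 7.4.3 category. Section 7.4.3 already implies this match; stating it makes the selection traceable.
4. Report which rule was applied to biopsies already taken, and say so where this was not recorded.

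The cost is the rewording of two sentences and one link in the data, with the signed amendment and the PRC and IRB approvals that Section 8.4 requires. Lesion SUVmax is already collected, and no patient procedure is added.

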5.1.2 Study Calendar for Sub-Cohort A2

Period / Procedure	Screening (Within 24 weeks after the start of current systemic therapy)	Follow up Response Monitoring 8 weeks (+/- 4 weeks)	Follow up PET 16 weeks (+/- 8 weeks) Following Treatment Initiation ⁷	Disease Progression by PCWG3
Informed consent	X			
Baseline conditions	X			
Concomitant medications	X			
Demographics	X			
Serum PSA ¹	X	X	X	X
Performance status	X			
LDH, CBC + diff, Liver function tests	X			
Disease assessment by cross sectional imaging	(X) ²	X ³	X ⁴	X ³
⁶⁸ Ga-PSMA-11 PET/CT or PET/MRI	(X) ^{5,6}		X	X (Optional)

¹ Response monitoring with respect to serum PSA will occur per standard of care and provider discretion. A minimum of two serum PSA values are required including: at baseline prior to initiation of systemic treatment (+/- 12 weeks), and at 16 weeks (+/- 8 weeks).

² Prior cross-sectional imaging of the chest/abdomen/pelvis (CT or MRI) performed within 12 weeks of the baseline ⁶⁸Ga-PSMA-11 PET scan (including paired CT or MRI obtained with baseline PET scan) may serve as a baseline and does not need to be repeated.

³ Response monitoring with respect to conventional imaging will occur per standard of care and provider discretion.

⁴ Cross-sectional imaging of the chest/abdomen/pelvis (CT or MRI; with IV contrast if medically permissible), including paired CT or MRI obtained with PET scan. Patients who underwent PET/CT at baseline should have same imaging modality performed during follow-up, and likewise patients who underwent PET/MR at baseline should have same imaging modality performed for follow up PSMA PET imaging.

⁵ A ⁶⁸Ga-PSMA-11 PET scan performed prior to study enrollment may serve as a baseline PSMA PET if performed within 12 weeks prior to the start of current systemic therapy. This scan is required within window as part of eligibility requirements (See [Section 3.3.1](#)). Patients must also have an on-treatment PSMA PET within 16 weeks (+/-8 weeks) after starting treatment.

⁶ At least one metastatic lesion with PSMA uptake at or above that of the blood pool will be required for study entry.

⁷ Specific timing of follow up PET to be determined based on modality of therapy (see [Section 5.3.6](#)).

